**Impaired Control Scale-Failed Control (ICS-FC)**

- The Impaired Control Scale is a 25-item scale that is used to measure the severity of alcohol dependence with respect to dimensions such as impaired control over drinking, awareness of compulsion to drink, etc. (Heather, Booth, & Luce, 1998).

**Alcohol Dependence Scale (ADS)**

- The ADS has been used widely and found to have excellent predictive value with respect to DSM diagnosis (Kivlahan, Sher, & Donovan, 1989) and will be used to assess severity of alcohol use symptoms.

**Pennsylvania Alcohol Craving Scale (PACS)**

- The PACS (Flannery, Volpicelli, & Pettinati, 1999) is a 5-item measure that will provide a measure of craving at each session.

**Drug Use Questionnaire**

- The Drug Use Questionnaire assesses individual behavior with regard to frequency and quantity of drug use. This measure will be used to assess whether smoking

---

and drug use behavior changes during the course of clinical trial.

**Beck Depression Inventory-II (BDI-II)**

- The BDI-II (Beck et al., 1996) is a 21-item measure of depression symptom severity in the past two weeks. BDI-II scores range between 0 and 63, with categorical depression ratings of “minimal” (0–13), “mild” (14–19), “moderate” (20–28), and “severe” (29–63). The BDI-II will be administered at baseline and at last follow-up to examine changes in comorbid depression and co-vary baseline differences if necessary.

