#### **Self-Report Outcome Measures (Baseline, Week 4, 8, 20, 32).**

- Heavy Drinking Days (HDD), Drinks per Drinking Day (DDD), and Percent Days Abstinent (PDA) as well as any comorbid drug use (e.g., tobacco use) will be obtained at each assessment using the Timeline Follow Back (TLFB), which is a calendar-based assessment of daily alcohol and drug use (Sobell et al., 1979). The TLFB has been shown to have good psychometric characteristics among a variety of drinker groups and can generate variables that provide a wide range of information about an individual's drinking (e.g., pattern, variability, and magnitude of drinking). HDD is the primary behavioral outcome that will be analyzed. However, secondary outcome measures of interest will also be collected.
- The Impaired Control Scale – Failed Control (ICS-FC) is a 25-item scale that is used to measure the severity of alcohol dependence with respect to dimensions such as impaired control over drinking, awareness of compulsion to drink, etc. (Heather, Booth, & Luce, 1998).
- The Alcohol Dependence Scale (ADS) has been used widely and found to have excellent predictive value with respect to DSM diagnosis (Kivlahan, Sher, & Donovan, 1989).
- The Pennsylvania Alcohol Craving Scale (PACS) is a 5-item measure of craving that will be completed at baseline and at each follow-up session to provide a measure of craving (Flannery, Volpicelli, & Pettinati, 1999). In a recent study, the PACS was found to be a

slightly better predictor of drinking as compared to the OCDS and AUQ (Flannery, Poole, Gallop, & Volpicelli, 2003).

- The Drug Use Questionnaire assesses individual behavior with regard to frequency and quantity of drug use. This measure will be used to assess whether smoking and drug use behavior changes during the course of clinical trial.
- The Beck Depression Inventory-II (BDI-II) consists of 21 scaled statements designed to assess symptoms of depression, with a coefficient alpha of .91 (Beck, Steer, & Carbin, 1988) The BDI-II will be administered at baseline and at last follow-up to examine changes in comorbid depression and covary baseline differences if necessary.
- The Beck Anxiety Inventory (BAI; Beck et al., 1988) consists of 21 items, each describing a common symptom of anxiety. The items are summed to obtain a total score that can range from 0 to 63. The BAI will be administered to examine comorbid anxiety and covary baseline differences if necessary.

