### **Criteria for inclusion in the study are:**

1. Must be between the ages of *21 and 60* and provide informed consent;
2. Have a primary DSM-V diagnosis of alcohol use disorder;
3. Must be within 10 days of last drink;
4. Must have been drinking heavily (criteria dependent upon individual's age, gender, and BMI) for a consistent period of time;
5. Must have a breath alcohol level of 0 at screening (to sign consent form);
6. Not currently taking any medications for the treatment of psychiatric disorders, including substance use disorders, mood disorders, and psychosis;
7. Female subjects must not be pregnant, as indicated by a pregnancy test which will be administered at baseline (tests will be re-administered at the 32 week session prior to the MR scan);
8. Must not be positive for sedatives, opiates, cocaine, or amphetamine on drug screen at baseline;
9. Must not meet criteria for psychotic disorder, bipolar disorder, or a major depressive episode;
10. Must not have a Beck Depression Inventory (BDI) score of more than 28 (29-63 indicates severe depression);
11. Must not rate 2 or higher on BDI question 9 (assessment of suicidality);
12. Must have a Clinical Institute Withdrawal Assessment (CIWA) score less than 8 (indicating no need for medical detox). If CIWA is greater than 8, patient will be referred to detox and only accepted into study after detox is successfully completed.
13. Must have expressed a desire during their initial screen to reduce the number of drinks they regularly consume

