### **Follow-up Assessment I (20 weeks)**

At this follow-up session, all subjects will take a BAC test, complete a set of self-report outcome measures and provide a blood sample. Subjects will be compensated \$50 for completing this assessment (\$30 for completing self-report measures and \$20 for providing blood samples). For subjects who are unable to come into the laboratory, the option of completing self-report measures online (via Qualtrics) will be provided for a \$30 compensation.

Participants who are unable to come into the laboratory will be sent an email, with an anonymous link to the same Qualtrics survey that would be administered at the follow-up assessments. All surveys are administered via Qualtrics and, thus, participants will already be familiar with navigating this online survey. The email will include the following instructions:

As our study staff noted, your progress since finishing treatment is extremely important for us to understand how alcohol treatments work, and why they may work better for some individuals than others. Therefore, regardless of whether you feel you have improved, declined, or had no changes since completing treatment, your responses are equally valuable. To reimburse you for your time, we will provide a \$30 gift card.

If you choose to proceed, here is the link to your survey: [INSERT LINK]

After clicking the link, please enter your study ID and treatment condition (see below). Please fill out this survey alone to ensure focus and anonymity. In addition, you may discontinue participation or refuse to answer any questions without penalty. Once you have completed the survey, study staff will be notified and you will receive your compensation within one week.

Your study ID is: [INSERT ID]

Your treatment condition is: [INSERT MBRP or RP]

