**Questionnaire Measures**  
**Collected at Baseline, 4, 8, 20,**  
**32 weeks**

**Timeline Follow Back (TLFB)**

- The TLFB (Sobell, Maisto, Sobell, & Cooper, 1979) is an assessment method that obtains estimates of daily alcohol, cigarette, and drug use. The TLFB has been shown to have good psychometric characteristics with a variety of drinker groups and can generate variables that provide a wide range of information about an individual's drinking (e.g., pattern, variability, and magnitude of drinking). This instrument requires subjects to recall from memory the number of drinks consumed for each day over the prior 30 days as well as their use of tobacco products and recreational drugs. Studies with alcoholics have shown this instrument to be reliable in assessing drinking frequencies and other behaviors such as arrests and hospitalizations (Sobell et al., 1979).

---

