Lastly, a potential risk that the study team will be prepared to manage is participant endorsement of thoughts of suicide on the Beck Depression Invention (BDI-II). The BDI-II is used to measure depression symptomatology. Item number 9 from the BDI-II inquires about “suicidal thoughts or wishes” that participants may or may not be experiencing. In order to ensure the safety of our participants, a staff member will check the participant’s response to item number 9 of the BDI-II before the participants leaves the building. If a participant has either responded “I would like to kill myself” or “I would kill myself if I had the chance,” the research team member will immediately notify [name] (a licensed clinical psychologist). [name] or a master’s-level clinician will immediately assess the participant for imminent suicide risk and provide him/her with a list of psychological services referral contacts. After the participant has been assessed for risk, the study coordinator will use the CU CHANGE lab’s previously IRB approved ‘Suicide Ideation Protocol’ to connect the participant with an appropriate referral resource (i.e., 911 if in imminent danger, Boulder County Mental Health Center (BCMHC) if the participant is a community member, or Wardenburg Health Center and/or BCMHC if the participant is a CU Boulder student, staff, or faculty member). [name] himself or a research team member will follow up with [name] to ensure that all of the necessary measures had been taken to protect the safety of the participant and determine whether or not it is safe for the participant to continue their involvement in the study. If it is determined that the participant is at imminent risk and should not continue participating in the study, [name] will contact the participant and explain that for their safety, the research team does not feel that it is safe for him/her to continue participating in the study and will also answer any questions the participant may have about this decision.

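### The BDI-II item 9 suicide check is tied to leaving the building, so surveys completed off site, chiefly by emailed link at week 32, have no stated review

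*Combined protocol and SAP*

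**What the plan says.** **The safety rule.** Section XVIII has a staff member check the participant's "response to item number 9 of the BDI-II before the participants leaves the building". Two named responses expressing suicidal intent lead to immediate notification of a licensed clinical psychologist and an immediate risk assessment by that psychologist or a master's-level clinician. The lab's previously approved Suicide Ideation Protocol is then used "to connect the participant with an appropriate referral resource".

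**The emailed-link route.** Section XI, Follow-up Assessment I (20 weeks), provides: "Participants who are unable to come into the laboratory will be sent an email, with an anonymous link to the same Qualtrics survey" used at the follow-up visits. The email asks the participant to complete the survey alone and to enter a study ID. It says that staff will be notified on completion and that payment follows within a week. Follow-up Assessment II (32 weeks) sends the same email.

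**The remote version.** The COVID-19 procedures at the end of Section XI move every assessment off site. A research assistant is on Zoom while the questionnaires are completed at baseline and weeks 4 and 8. At weeks 20 and 32 the text says the questionnaires are completed through a link, and the table gives the location as Remote/Zoom.

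**The BDI-II schedule.** In Section IV the scale sits in a list headed "Self-Report Outcome Measures (Baseline, Week 4, 8, 20, 32", but its own entry says it is given "at baseline and at last follow-up to examine changes in comorbid depression and covary baseline differences if necessary". Section XI repeats the pattern: the block heading begins "Collected at Baseline, 4, 8, 20" and goes on to 32 weeks, while the entry reads "The BDI-II will be administered at baseline and at last follow-up to examine changes in comorbid depression and co-vary baseline differences if necessary".

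**Entry.** Inclusion criterion 11 is "Must not rate 2 or higher on BDI question 9 (assessment of suicidality". Criterion 10 allows a BDI score up to 28.

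**The concern.** The item 9 rule is built around a physical visit, yet the plan allows surveys to be completed where there is no building to leave. In the text shown, Section XVIII is the step that turns an item 9 response after entry into a clinician assessment. Where that step cannot be carried out as written, a participant could report suicidal intent and nothing in the protocol would say who reads the answer or by when.

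The population makes this a practical matter. Participants may enter with any score in the moderate band of 20 to 28. What is at stake is participant safety. The primary analysis of heavy drinking days does not depend on it.

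**Working it through.** The plan states no figure to reproduce, so this is a comparison of sections.

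**Step 1: when can item 9 arrive by emailed link?**
- BDI-II weeks if its entries govern: {0, 32}.
- BDI-II weeks if the list headings govern: {0, 4, 8, 20, 32}.
- Emailed-link weeks: {20, 32}.
- Overlap with the entries: {32}, which is 1 of 2 administrations.
- Overlap with the headings: {20, 32}, which is 2 of 5 administrations.

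Week 32 is in both overlaps and week 20 in only one. These counts apply only to participants who use the link, and the documents do not say how many will.

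**Step 2: what is stated on each route?**

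| Route | Staff contact stated | Item 9 review stated |
|---|---|---|
| In-person visit | Staff on site | Yes, before departure |
| Emailed link, week 32 (and 20 on the headings reading) | Notice of completion only | None, and no review time |
| Remote, baseline | Research assistant on Zoom | No safety check stated, but criterion 11 requires item 9 to be read for eligibility |
| Remote, weeks 4 and 8 (headings reading only) | Research assistant on Zoom during the survey | None stated, but a live check is feasible |
| Remote, week 32 (and 20 on the headings reading) | Listed as Remote/Zoom; attendance during the survey not stated | None stated |

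**Step 3: was a remote version of the check written elsewhere?** Remote text is supplied for the study design, recruitment, compensation, consent and procedures sections. Section XVIII has none, and the remote procedures in Section XI do not mention item 9.

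**Step 4: do other safeguards reach an emailed-link user at week 32?**
- Weekly supervised therapy ends at week 8, which is 32 - 8 = 24 weeks earlier.
- The coordinator contacts patients between follow-up visits, but this is described under attrition.
- Section XI attaches the post-scan assessment and the week-33 therapist visit to the scan, which is done in person at week 32.
- The DSMB reviews adverse events and differences between arms every three months.

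None of these is described as reading an individual's item 9 answer.

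**The case against.** The strongest reply is that only the phrase about the building fails, while the check itself can be done. Staff are told when a link survey is complete, and the study ID makes the answer traceable. A research assistant is on Zoom for three of the five remote assessments, and the other two are listed as Zoom visits. At baseline, item 9 has to be read to decide eligibility, and the responses that trigger Section XVIII appear to be those that criterion 11 excludes. The Suicide Ideation Protocol is not in the documents and may contain an off-site procedure.

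Most of this stands for the remote version, where it reduces the gap to missing wording on review and escalation. It does less for the emailed link. A completion notice is not a review, no time is set, and no staff member is present. As Section XVIII describes it, the Suicide Ideation Protocol is used after the risk assessment, so someone must already have read item 9.

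A reader might infer two stronger points that the documents do not support.
- **That the BDI-II schedule is a contradiction leaving participants unscreened during treatment, so the scale must be given at all five assessments.** Both entries give the same explicit rule, and a specific entry can override a list heading: the Mindfulness Practice Questionnaire sits in the same lists but is collected weekly. The stated purpose, change in depression, needs only two time points. Participants also see a supervised therapist every week through week 8.
- **That every remote administration goes unchecked.** The baseline eligibility review and the Zoom attendance at baseline and weeks 4 and 8 rule out that count.

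**Conclusion.** The concern holds in a limited form. The item 9 check cannot be carried out as written on an off-site route that the plan itself allows, and for emailed-link surveys nothing replaces it. Week 32 is affected whichever BDI-II schedule applies. The remote version has the same omission with less practical consequence.

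This rests on two assumptions. First, the emailed week-32 survey carries the BDI-II, which follows from its being the same survey as at the visit. Second, the unseen Suicide Ideation Protocol does not already set an off-site review of item 9; if it does, a cross-reference would largely close the gap. No risk can be attached, because the documents give neither the number of link users nor a rate of item 9 endorsement. Sample size, power and the primary analysis are unaffected. The change should be made because it is a safety provision and costs little.

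**What to change.** In Section XVIII, add an off-site rule. For surveys completed on Zoom, staff review item 9 before the session ends. For emailed-link surveys, staff review it on the same day they are notified of completion, identifying the participant through the study ID. Either review is followed by the same clinician assessment and referral as on site.

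The cost is prompt reading of responses and a clinician who can be reached on those days. No visits or forms are added, and the completion notice and Zoom contacts already exist.

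As an editorial clarification only, align the list headings in Sections IV and XI with the BDI-II entries, for example by giving the scale its own line for baseline and week 32. The investigators may choose to give it at all five assessments instead. Starting from the two-visit schedule, that adds 3 x 21 = 63 items per participant and at most 3 x 226 = 678 forms. This, and checking item 9 before the second scan, are optional preferences.

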**Beck Anxiety Inventory (BAI)**

- The BAI (Beck & Steer, 1990) consists of 21 items, each describing a common symptom of anxiety. The items are summed to obtain a total score that can range from 0 to 63. The BAI will be administered to examine comorbid anxiety and co-vary baseline differences if necessary.

**Pain Interference - SF 8a**

- The Pain Interference item bank is from the National Institutes of Health (NIH) and is part of the Patient Reported Outcomes Measurement Information System (PROMIS). The Pain Interference SF-8a, is a 8-item short-form questionnaire that measures the self-reported consequences of pain on relevant aspects of one’s life. This includes the extent to which pain hinders engagement with social, cognitive, emotional, physical, and recreational activities (Amtmann et al., 2010).

---

**The Five Facet Mindfulness Questionnaire**

- The Five Facet Mindfulness Questionnaire (Baer et al., 2006) will determine the extent to which MBRP increases mindfulness practice as a proximal mediator of the effects of the intervention. These data will be used as a manipulation check.

**Mindfulness Practice Questionnaire**

- The extent to which patients engage in key aspects of mindfulness will be collected using the 10 item Mindfulness Practice Questionnaire (e.g., [name], Lustyk, & [name], 2013) on a weekly basis.

**Comprehensive Inventory of Mindfulness Experiences (CHIME)**

- The CHIME (Bergomi, Tschacher, & Kupper, 2015) consists of three items and will determine the number of minutes of mindfulness practice per week each patient is currently engaging in. Minutes of current meditation practice will be calculated using the following compound variable: (weekly frequency x average session duration). The data will be used to co-vary for patients who are already engaging in frequent mindfulness meditation practice at baseline if necessary.

**Multidimensional Personality Questionnaire – Stress Reaction**

- The Multidimensional Personality Questionnaire (Tellegen, 1982, Tellegen & Waller, 2008) consists of 18 True/False items of statements describing negative emotionality and stress reaction. The questionnaire will be administered to examine comorbid negative emotionality and used to co-vary baseline differences if necessary.

---

**Response Styles  
Questionnaire -  
Ruminative Response  
Scale**

- The Ruminative Response Scale (Treynor, Gonzalez, & Nolen-Hoeksema, 2003) consists of 22 items scoring how often the patient engages in ruminative thinking associated with depression. The data will be used to examine comorbid negative emotionality and used to co-vary baseline differences if necessary.

**Emotion Regulation  
Questionnaire (ERQ)**

- Emotion Regulation Questionnaire (ERQ) is a 10-item scale that is designed to assess individual differences in the habitual use of two emotion regulation strategies: cognitive reappraisal and expressive suppression (Gross, John, 2003).

**Effortful Control Scale –  
Full Scale**

- The Effortful Control Scale (Derryberry & Rothbart, 1988, Evans & Rothbart, 2007) consists of 35 items that measure the degree to which the patient exhibits behavioral control. The data will be used to co-vary baseline differences in behavioral control if necessary.

**Drinking Motives  
Questionnaire**

- The Drinking Motives Questionnaire (Cooper, 1994, Kuntsche et al., 2006, Young-Wolff et al., 2009) consists of 20 items used to assess patients' varying motives for drinking alcohol. The Drinking Motives Questionnaire will be used to assess whether motives for drinking alcohol change from baseline following treatment.

---

**Quantity/Frequency of Alcohol use**

- Alcohol use will be evaluated with a variation of the measure used by White and Labouvie (1989). First, participants will be asked if they have ever had an alcoholic drink (with instructions that define one alcoholic drink as “one beer, one glass of wine, or one serving of hard liquor either by itself or in a mixed drink”). Those (likely well over 90%) who answer that they have previously had alcohol before will be asked to rate: (1) their frequency of use in the last three months on a 9-point scale ranging from “never” to “every day”, (2) their typical quantity of drinks in one sitting on a 10-point scale ranging from “no drinks” to “more than 20 drinks”, and (3) their frequency of getting drunk when drinking in the past three months on a 5-point scale ranging from “never” to “always.”

**Alcohol Use Disorders Identification Test (AUDIT)**

- The AUDIT (Saunders, Aasland, Babor, De La Fuente & Grant, 1993) is used to detect less severe problem drinkers and addresses both current problems (problems within the last 3 months) and problems across an individual’s lifetime. The AUDIT consists of ten questions that cover such domains as alcohol consumption, drinking behavior, adverse psychological reactions, and alcohol-related problems.

**Prior Treatment Experiences Questionnaire (PTEQ)**

- Participants will be asked about their engagement in any 12-step programs (Tonigan, Miller & Conners, 1997), psychological services for alcohol and other

---

problems, and use of other self-help materials. At baseline, participants will be asked about lifetime engagement in treatment. Because this study will be recruiting a population of heavy drinkers, it will be important for us to know whether or not any of our participants have previously received treatment for alcohol abuse. In future analyses, this information (e.g., prior treatment history) will be used as a covariate.

